10.2. Study Candidate Screening

Subjects will be screened against the inclusion/exclusion criteria and if confirmed to meet all the requirements attainable per standard of care, will be eligible to be consented for enrollment into the study. Any non-standard of care assessments that must be conducted in order to complete the inclusion/exclusion criteria review will be completed after the subject has completed the informed consent process.

Subjects who do not meet the inclusion/exclusion criteria and were not enrolled into the study are considered screen failures. Information on screen failures will be captured in the source documentation and screening logs and should include reasons for screen failure. These screen failures will not count toward the enrollment ceiling.

If the subject has completed the informed consent process and met all inclusion/exclusion criteria, the subject will progress to the index procedure and follow-up phases of the study.

10.2.1. Strategies for Recruitment and Retention

Subjects will be recruited from clinician practice.

Subjects will be compensated for visit related expenses. The compensation will be modest in nature and approved by the reviewing IRB/EC.

10.3. Informed Consent

Prior to any study-related assessments, each subject must complete the informed consent process and sign an IRB/EC-approved informed consent document to participate in the study as described in the Declaration of Helsinki and ISO 14155:2020 (Clinical Investigation of Medical Devices for Human Subjects- Good Clinical Practice) and will be in accordance with all applicable laws and regulations. The informed consent form will describe the planned and permitted uses, transfers and disclosures of the subject's personal health information.

The subject or legally authorized representative (if approved by IRB/EC) will be given ample opportunity to inquire about details of the study to decide whether to participate in the study. Copies of the informed consent form will be provided to the subject and original documents filed at each study center as per regulatory requirements.

Once the subject voluntarily agrees to participate in the study, then the Study Visit Schedule will be followed per below and as outlined in Table 10.1-1.

10.4. Screening/Enrollment Visit

The Screening/Enrollment may occur prior to the Pre-Operative/Baseline Visit. At this visit, the assessments below must be completed:

- Informed Consent Process, including informed consent signature
- Review of Inclusion/Exclusion Criteria

Medical History

10.5. Pre-Operative/Baseline Visit |≤90 calendar days before Index Procedure|

The Pre-operative/Baseline Visit will occur prior to the subject having surgery. The assessments below must be completed prior to index procedure. This visit may be combined with the Screening/Enrollment Visit and may occur up to 90 calendar days prior to surgery.

- Demographics and physical examination
- Medical History
- 3-day eDiary
- 24-hour pad weight test
- Number of pads per day
- IQoL
- IIQ-7
- EQ-5D

10.6. Index Procedure [≤90 calendar days from Baseline]

All procedures are to be performed with the AMS 800 Artificial Urinary Sphincter. Concomitant procedures are not allowed. Physicians should follow the IFU during the procedure. The following data must be collected during the index procedure:

- Study device component information
- Estimated blood loss
- Anesthesia type
- Duration of procedure, defined as time of first incision to time of closure
- Assessment of adverse events and device deficiencies

Once enrollment is complete, each study site investigator will be sent one AMS tools questionnaire to complete based on the AMS tools used during the index procedures.

10.7. Device Activation [Approximately 30-45 days post index procedure] and Follow-up Procedures

Subjects will be scheduled for follow-up visits as outlined in Table 10.1-1 (Data Collection Study Schedule).

Every effort should be made to complete the follow-up visit within the window; however, if this is not possible, the site should attempt to complete the visit as soon as possible but before the next visit window opens. Follow-up visits will be considered missed once the visit window for the next follow-up visit opens. For the Month 12 visit, the visit is not considered missed until the last day of the visit window.

Page 32 of 62

Subjects will be scheduled for device activation approximately 4-6 weeks following the index procedure per standard of care. The following assessments will be attained 24 to 48 hours after the device activation:

- 24-hour pad weight test
- Adverse event and device deficiency collection

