9.3. Lost to Follow-Up

If a participant fails to contact the clinic for a required study visit, the site will attempt to contact the participant and reschedule the missed visit prior to the next visit window, and are encouraged to remind the participant on the importance of maintaining the assigned visit schedule and ascertain if the participant wishes to and/or should continue in the study.

Before the subject may be considered lost to follow-up, the investigator must make the following attempts to contact the subject:

- Three documented telephone attempts
- One certified letter

If the subject can be reached and no longer wishes to participate in the study, the Investigator shall document the reason for the withdrawal and complete the End of Study eCRF.

If subject is not able to be reached after the required attempts to contact the subject have been made and the subject has missed two consecutive follow-up visits within the 12-month follow-up schedule, or the subject has missed the final 12-month follow-up visit, the subject may be considered lost to follow-up. The Investigator should document in the subject's medical record the attempts to contact the subject and the reason for withdrawal.

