10.1. Data Collection

The data collection schedule is shown in Table 10.1-1. All study data will be recorded on source documentation and captured within Case Report Forms (CRFs) for the purposes of this study. Study data will be monitored by Boston Scientific or representatives and as applicable on a regular basis as outlined in the study Monitoring Plan.

Table 10.1-1: Data Collection Schedule

Procedure/Assessment	Screening / Enrollment Visit²	Pre-Operative / Baseline Visit (≤90 calendar days before index procedure)	Index Procedure (≤90 calendar days from screening visit)	Device Activation (30-45 calendar days post index procedure)	Follow-up Visits ⁴		
					3 Month Visit ⁵ (±6 Weeks)	6 Month Visit ⁵ (± 3 Months)	12 Month Visit ⁵ (± 3 Months)
Informed consent process, including informed consent signature and date	X						
Inclusion/Exclusion Criteria Review	X	X					
Demographics		X					
Physical assessment, including weight and height		X				X^6	X^6
Medical history ¹	X	X					
3-day eDiary		X				X	X
24-hour Pad Weight Test		X		X		X	X
# Pads per Day		X			X	X	X
IQoL (Urinary Incontinence Quality of Life)		X			X	X	X
IIQ-7 (Incontinence Impact Questionnaire)		X			X	X	X
EQ-5D (Health Status)		X					X
Patient Ease of Use Questionnaire						X	X
Index Procedure			X				
Assessment of Adverse Events and Device Deficiencies ³			X	X	X	X	X
End of Study							X

¹Medical History at baseline includes documented absence of urine culture.

²The Screening/Enrollment Visit and Pre-Operative/Baseline Visit may be combined and occur up to 90 calendar days prior to the study procedure with confirmed absence of infection.

³Reportable events include (procedure related) AEs, SAEs, SADEs, ADEs and device deficiencies. Adverse events that are not related to the device and not related to the procedure will not be collected; however, these assessments should be noted in the subject's medical records.

⁴Every effort should be made to do the follow-up visit within the window; however, if this is not possible, the site should attempt to complete the visit as soon as possible, but before the next visit window opens. Follow-up visits will be considered missed once the visit window for the next follow-up visit opens. For the Month 12 visit, the visit is not considered missed until the last day of the visit window. All follow-up visit windows start from the day of device activation.

₅Visits may be conducted in clinic or remote.

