10.8. Month 3 Follow-up Visit $f \pm 6$ weeks post device activation

The 3-month follow-up visit occurs 90 calendar days after the day of device activation, \pm 6 weeks.

Subjects can be contacted via a remote visit for their 3-month follow-up visit. A clinic visit is also allowed, though not required. Remote contacts must be documented in the subject's medical records.

Questionnaires cannot be completed over the phone. The site must mail the questionnaires to the subjects and the subjects should return the questionnaires to the site as soon as possible.

The following data will be collected at the 3-month visit:

- Number of pads per day
- IQoL
- IIQ-7
- Assessment of adverse events and device deficiencies

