10.9. Months 6 [\pm 3 Months] and 12 Visit [\pm 3 Months]

The 6-month follow-up visit occurs 180 calendar days after the day of device activation, \pm 3 months. The 12-month follow-up visit occurs 365 calendar days after the day of device activation, \pm 3 months. These visits may occur either remotely or in clinic.

Questionnaires cannot be completed over the phone. The site must mail the questionnaires to the subjects and the subjects should return the questionnaires to the site as soon as possible. Pads can be mailed to subjects and returned per the pad weight protocol or dropped off by the subject.

The following data will be collected at the 6-month and 12-month visits:

- Physical examination including height and weight (Note: If a remote visit is completed, the subject may self report his height and weight.)
- 3-day eDiary
- 24-hour pad weight test
- Number of pads per day
- IQoL
- IIQ-7

- EQ-5D (Month 12 only)
- Patient Ease of Use
- Assessment of adverse events and device deficiencies
- Study completion (12-month follow-up only)

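### The missed-visit and catch-up rule cannot be applied to Month 3, whose window overlaps Month 6, and the synopsis's 13.5-month participation disagrees with the Month 12 window (minor)

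*Combined protocol and SAP*

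**What the plan says.** **Missed and late visits.** Section 10.7 states: "Follow-up visits will be considered missed once the visit window for the next follow-up visit opens". For a visit that cannot be done in window, "the site should attempt to complete the visit as soon as possible but before the next visit window opens". Footnote 4 to Table 10.1-1 (Section 10.1) repeats both rules and counts every window from device activation. Only Month 12 is exempt; it is not missed until the last day of its own window. Section 9.3 similarly asks the site to "reschedule the missed visit prior to the next visit window". Among its conditions for loss to follow-up, Section 9.3 lists that "the subject has missed two consecutive follow-up visits within the 12-month follow-up schedule".

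**Windows.**
- Section 10.8: "The 3-month follow-up visit occurs 90 calendar days after the day of device activation", ± 6 weeks.
- Section 10.9: "The 6-month follow-up visit occurs 180 calendar days after the day of device activation", ± 3 months.
- Section 10.9: "The 12-month follow-up visit occurs 365 calendar days after the day of device activation", ± 3 months.

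**Participation.** The synopsis (Participant Duration) expects about 12 months from activation, and 13.5 months for a subject seen at the end of the window. It puts total study duration at about 44 months and does not show how that was built up.

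**The concern.** The missed-visit rule assumes that each window closes before the next one opens. That is true of Month 6 and Month 12 but not of Month 3 and Month 6. For Month 3 the next window opens at about the target day, so a visit not yet done is labelled missed while Section 10.8 still allows it. The instruction to catch up late visits before the next window opens leaves no days on which a late Month 3 visit could be done.

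A site that applies the missed-visit sentence could stop pursuing Month 3 at about day 90. It would then lose 3-month pads per day (a secondary endpoint), IQoL and IIQ-7 data that could still have been collected in window. Section 11.3 analyses available cases, so those values would not be recovered. The site could also record a missed visit that counts towards the two-visit condition in Section 9.3. Missed-visit counts would differ between sites according to which sentence each one follows.

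The 13.5-month figure is a separate mismatch: it understates the longest participation that the current Month 12 window allows.

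**Working it through.** **Inputs.** Target days 90, 180 and 365 after activation (Sections 10.8 and 10.9); half-widths 6 weeks = 42 days and 3 months (Table 10.1-1). The protocol does not define 3 months in days. I take 90 days, in line with Month 3 = day 90 and Month 6 = day 180. As a range I use calendar months, where three months span 89–92 days. Days are counted inclusively.

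**Windows (target ± half-width).**

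| Visit | 3 months = 90 days | Calendar months |
|---|---|---|
| Month 3 | 48 to 132 (85 days) | same |
| Month 6 opens | 180 − 90 = 90 | 88–91 |
| Month 6 closes | 180 + 90 = 270 | 269–272 |
| Month 12 opens | 365 − 90 = 275 | 273–276 |
| Month 12 closes | 365 + 90 = 455 | 454–457 |

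**Month 3 days on or after the opening of Month 6.** 132 − 90 + 1 = 43 of 85, or 50.6%. With calendar months: 132 − 91 + 1 = 42 (49.4%) to 132 − 88 + 1 = 45 (52.9%).

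**Catch-up days (after a visit's own window closes, before the next opens).**
- Month 3: none. Its window closes on day 132, which is 132 − 90 = 42 days after Month 6 opened.
- Month 6: days 271–274, which is 4 days; 0–3 days with calendar months.

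The rule is therefore coherent for Month 6, if tight, and the exception covers Month 12. Only Month 3 fails.

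**Participation.** I first tried to reproduce 13.5 months.
- 12 months + 6 weeks ≈ 12 + 1.5 = 13.5. This needs a ± 6-week window at Month 12; the current text gives that width only to Month 3.
- 12 months + 45 days from implant to activation = 13.5. But the synopsis counts from activation and attributes the figure to the visit window.
- With the current Month 12 window: 12 + 3 = 15 months (day 455), which is 15 − 13.5 = 1.5 months more than stated.

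**Against the 44-month total.** Adding 24 (enrolment) + 3 (90 days from baseline to procedure) + 1.5 (45 days to activation) + 15 gives 43.5. With 13.5 in place of 15 the sum is 42.0. This reconstruction is mine. Section 7.1 counts the 24 months from activation of the final centre, so time before that is not in the sum. It settles nothing about the 44.

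**The case against.** The strongest reply is that Section 10.7 reads as a sequence: do the visit in window; failing that, do it late; failing that, it is missed. On that reading the word applies only to visits not done, and a Month 3 visit completed on day 100 is simply in window under Section 10.8. This stands. A reader might infer that completed visits on days 90–132 are both valid and missed, so that half of the Month 3 window is void. The documents do not support this: Section 10.8 allows those days, although nothing sets that permission against the missed-visit sentence. What remains is the visit not yet done, and the empty catch-up period. The sequential reading resolves neither.

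It is also fair to say that the consequences are limited. A reader might infer that a mislabelled Month 3 visit makes a subject lost to follow-up. It cannot do so alone. Section 9.3 also requires failed contact after three documented calls and a certified letter, plus a second consecutive missed visit or a missed Month 12, and even then says only that the subject may be so classed. The 3-month outcomes are descriptive. The Kaplan-Meier estimates for serious adverse events and revision use fixed days 90, 180 and 365 (Sections 11.1.2.1.1 and 11.1.2.2.1), and reportable events are collected throughout participation (Section 18.1), so they do not depend on visit labels.

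On participation, a reader might infer that 13.5 is left over from a narrower window, or that the 44-month total proves 15 is right. The revision history says that windows were extended but gives no earlier width, and the 44 has no stated derivation. Neither inference is needed: the current synopsis and the current Month 12 window disagree as they stand.

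**Conclusion.** The point holds as a minor internal inconsistency, wrong as written, in two parts.

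1. For Month 3, an uncompleted visit is called missed at about its target day while roughly half its window remains, and the catch-up instruction cannot be followed. The count of 43 of 85 days assumes that 3 months is 90 days. Under calendar months it is 42–45, and the conclusion is the same.
2. Participation to the end of the Month 12 window is 15 months from activation, not 13.5, if ± 3 months is intended.

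Any loss of 3-month data depends on sites acting on the missed-visit sentence rather than on Section 10.8. The primary endpoint, sample size, Kaplan-Meier safety estimates and 12-month results are not affected, and no analysis uses the 13.5-month figure.

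**What to change.** Reconcile Section 9.3, footnote 4 to Table 10.1-1 and Section 10.7 with Sections 10.8 and 10.9, without altering any window. For example:

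- A Month 3 or Month 6 visit is missed only at the later of its own window closing and the next window opening. With 90-day quarters, Month 3 becomes max(132, 90) = day 132, and Month 6 stays at max(270, 275) = day 275.
- The catch-up instruction, including its counterpart in Section 9.3, applies only where a visit's window closes before the next one opens, and so not to Month 3.
- The existing Month 12 exception is kept explicitly, because Month 12 has no next window.
- The site records which scheduled visit each completed visit represents.

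In the synopsis, reconcile the 13.5 months with the Month 12 window (15 months if ± 3 months is intended), and confirm whether the 44-month total is consistent with it.

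The cost is wording only, with no added visits or analyses. Two limits remain. Month 3 and Month 6 visits can still both fall on days 90–132, because that follows from the windows themselves. Partial visits must be labelled by the site, because pads per day, IQoL and IIQ-7 are common to both visits and cannot identify which one was done.

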10.8. Month 3 Follow-up Visit $f \pm 6$ weeks post device activation

The 3-month follow-up visit occurs 90 calendar days after the day of device activation, \pm 6 weeks.

Subjects can be contacted via a remote visit for their 3-month follow-up visit. A clinic visit is also allowed, though not required. Remote contacts must be documented in the subject's medical records.

Questionnaires cannot be completed over the phone. The site must mail the questionnaires to the subjects and the subjects should return the questionnaires to the site as soon as possible.

The following data will be collected at the 3-month visit:

- Number of pads per day
- IQoL
- IIQ-7
- Assessment of adverse events and device deficiencies

10.9. Months 6 [\pm 3 Months] and 12 Visit [\pm 3 Months]

The 6-month follow-up visit occurs 180 calendar days after the day of device activation, \pm 3 months. The 12-month follow-up visit occurs 365 calendar days after the day of device activation, \pm 3 months. These visits may occur either remotely or in clinic.

Questionnaires cannot be completed over the phone. The site must mail the questionnaires to the subjects and the subjects should return the questionnaires to the site as soon as possible. Pads can be mailed to subjects and returned per the pad weight protocol or dropped off by the subject.

The following data will be collected at the 6-month and 12-month visits:

- Physical examination including height and weight (Note: If a remote visit is completed, the subject may self report his height and weight.)
- 3-day eDiary
- 24-hour pad weight test
- Number of pads per day
- IQoL
- IIQ-7

- EQ-5D (Month 12 only)
- Patient Ease of Use
- Assessment of adverse events and device deficiencies
- Study completion (12-month follow-up only)

10.10. Study Completion

All subjects completing the 12-month follow-up visit will be considered to have completed the study.

Upon completion of the study, all adverse events indicated as "ongoing" should be changed to one of the following outcomes:

- Not Recovered/Not Resolved
- Resolved
- Resolved with sequelae
- Unknown

The outcome of "unknown" should only be used for subjects who are lost to follow-up. Whenever possible, sites should enter a reason for each ongoing/unresolved adverse event at time of study exit.

10.11. Revision Surgery

It is recognized that during the course of the study, there is a possibility subjects may require a medical revision of the implant for events including but not limited to infection, erosion, and mechanical malfunction.

A medical revision is defined as a secondary surgery to modify or replace the initially implanted device. A replacement is a subset of medical revision, defined as removal of one or more components of the AMS 800 and/or implantation of a new component. Components include the cuff, pump, and PRB.

Any subject who receives a medical revision should return to the clinic for the next regular study visit as per his original schedule.

10.12. Source Documents

It is preferable that original source documents are maintained, when available. In lieu of original source documents, certified copies are required to be maintained. A certified copy is a copy (irrespective of the type of media used) of the original record that has been verified (i.e., by a dated signature or by generation through a validated process) to have the same information, including data that describe the context, content, and structure, as the original.

11. Statistical Considerations

11.1. Endpoints

11.1.1. Primary Endpoint

The primary endpoint is defined as treatment success based on the 24-hour pad-weight test. A 50% or greater reduction in pad-weight from baseline to 12 months post-device activation is considered a treatment success.

11.1.1.1. Hypotheses

The study will evaluate whether the proportion of subjects experiencing a treatment success exceeds 65% at 12 months. The null and alternative hypotheses for this evaluation are

H₀: $p \le 65\%$ H₁: p > 65%

where p is the proportion of subjects who are a treatment success at 12 months.

11.1.1.2. Sample Size

The sample size calculation is based on an assumption that the treatment success rate is 80%⁴. With a one-sided type I error of 0.025 and a type II error of 0.10 (90% power), a sample size of 96 subjects are needed to demonstrate the proportion of subjects who are a treatment success exceeds 65%. Assuming a 20% attrition rate, at least 120 subjects with AMS 800 AUS procedure are required.

11.1.1.3. Statistical Methods

The hypotheses will be evaluated using a one-sided exact binomial test. In addition, a two-sided 95% exact (Clopper-Pearson) confidence interval will be presented. Sensitivity analysis to missing data will be performed using tipping-point analysis. If a medical revision is performed due to efficacy reasons at or prior to the 12 month visit, then the subject is considered as experiencing a treatment failure.

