activation, 6 months, and 12 months post device activation compared to baseline Reduction in # of pads per day	more stringent measurement than primary endpoint
1 1	01.1
at 3 months, 6 months and 12 months post-device activation compared to baseline	Objective measurement of number of incontinence episodes per day. Common endpoint to assess urinary incontinence ^{9,10}
Comparison of Pressure Regulating Balloons by subgroup analysis Change in numbers of stress urinary incontinence episodes, fluid intake, urgency urinary incontinence episodes, and frequency of urination based on 3-day electronic diary at 6 months and 12 months post device activation compared to baseline	Compare different pressure regulated balloons Gather patient reported outcomes on device ^{9, 10}
Change in quality of life at 3 months, 6 months, and 12 months compared to baseline, as measured by the following questionnaires – IQoL, IIQ-7, EQ5D Subject Ease of Use questionnaire	Gain information on patient satisfaction and improvement in quality of life using validated questionnaires ¹⁰ Gain information specific to the patient's use of the
	at 3 months, 6 months and 12 months post-device activation compared to baseline Comparison of Pressure Regulating Balloons by subgroup analysis Change in numbers of stress urinary incontinence episodes, fluid intake, urgency urinary incontinence episodes, and frequency of urination based on 3-day electronic diary at 6 months and 12 months post device activation compared to baseline Change in quality of life at 3 months, 6 months, and 12 months compared to baseline, as measured by the following questionnaires – IQoL, IIQ-7, EQ5D Subject Ease of Use

7. Study Design

The study is a single arm, prospective, multi-center study with 12-month follow-up following device activation.

Page 21 of 62

The primary endpoint will be evaluated once all Intent-To-Treat (ITT) subjects have completed the 12-month study visit. All subjects will be followed to month 12, until study completion, or until discontinuation prior to month 12. All study procedures will be standardized for uniformity.

Physician specialty and site procedure location (such as private-practice, hospital, academic medical center, etc.) will be recorded in the site selection questionnaire.

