11.2. General Statistical Methods

The Intent-to-Treat (ITT) subject population includes all subjects who provide written informed consent to be enrolled into the study, and have a surgery initiated (defined as the first incision).

The As Treated (AT) Population includes all subjects for whom implantation of the device is successful.

The Per Protocol (PP) population includes all subjects in the AT Population who meet all eligibility criteria and have no major protocol deviations.

The endpoint analyses will be performed for the ITT population. The AT and PP populations will be evaluated as sensitivity analyses for the primary endpoint, and the safety outcomes will also be assessed using AT population.

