11.3. Data Analyses

The analyses will include only the available cases unless specified otherwise. Presentation of summary statistics for continuous variables will include N, mean, median, standard deviation, minimum, and maximum values. For categorical variables, the number and percentage under each category will be presented.

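### The primary ITT test gives no outcome to men without a working device who return no 12-month pad test; if they are failures, the success rate is biased upward, in favour of exceeding 65%

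*Combined protocol and SAP*

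**What the plan says.** - **Analysis set.** Section 11.2: "The endpoint analyses will be performed for the ITT population". Sections 9.4 and 11.2 both start ITT at first incision, so a man whose implantation is begun and abandoned belongs to it.
- **Outcome.** Section 11.1.1: "A 50% or greater reduction in pad-weight from baseline to 12 months post-device activation is considered a treatment success".
- **Clock.** Table 10.1-1, footnote 4: "All follow-up visit windows start from the day of device activation". Section 10.9: "The 12-month follow-up visit occurs 365 calendar days after the day of device activation".
- **Missing values.** Section 11.3: "The analyses will include only the available cases unless specified otherwise". Section 11.1.1.3 adds a tipping-point analysis as a sensitivity analysis, and section 11.2.1 refers to it again.
- **Forced failure.** The one such rule, in section 11.1.1.3, applies to a particular kind of revision: "If a medical revision is performed due to efficacy reasons at or prior to the 12 month visit". The plan does not say which reasons count as efficacy reasons.
- **Follow-up.** Section 7: "All subjects will be followed to month 12, until study completion, or until discontinuation prior to month 12". Section 9.4 likewise puts ITT men on the study follow-up schedule.
- **Size.** Section 11.1.1.2 asks for 96 men, then: "Assuming a 20% attrition rate, at least 120 subjects with AMS 800 AUS procedure are required".

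**The concern.** The hypothesis concerns the proportion of subjects who succeed, and the stated set is everyone with a first incision. A man who was never implanted or never activated has no activation date, so his 12-month visit has no defined time. If he returns no pad test, the available-case default removes him, and nothing in section 11.1.1.3 puts him back. The same happens to a man whose device is explanted and not replaced and who returns no test, unless his surgery counts as a revision for efficacy reasons.

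Such men are unlikely to have halved their leakage. Leaving them out moves the estimate from success among all men operated on towards success among men who had a device activated and came back with a test. That shift favours meeting the goal. Section 11.2.1 calls the primary analysis conservative. The exact test is conservative because the binomial is discrete, but this omission works the other way.

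**Working it through.** **Inputs.** From sections 11.1.1.1 to 11.1.1.3: null rate 0.65, assumed rate 0.80, one-sided 0.025, exact binomial test, 96 tested, 120 treated. Assumption: *k* men per 120 have no working device, return no test and are failures. The documents give no value for *k*; 0 to 6 is used here.

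**1. The plan's own figures.** The critical value is the smallest r with P(X ≥ r | n, 0.65) ≤ 0.025. For n = 96, r = 72 (75.0%), with exact error 0.0236 and power P(X ≥ 72 | 96, 0.80) = 0.909. No smaller n checked (88 to 95) reaches 0.90. Attrition: 96/(1 − 0.20) = 120. Both planned numbers reproduce.

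**2. False success as written.** If the true ITT rate is 0.65 and the *k* men are all failures, the rate among the others is 0.65/(1 − k/120). The test then passes with probability P(X ≥ 72 | 96, that rate).

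| k per 120 | Rate among the others | False success as written |
|---|---|---|
| 0 | 0.650 | 2.4% |
| 1 | 0.655 | 3.0% |
| 3 | 0.667 | 5.0% |
| 6 | 0.684 | 9.9% |

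**3. Result near the planned rate.** 77/96 = 80.2%. With 7 failures added, 77/103 gives p = 0.022 and passes. With 8, 77/104 gives p = 0.032 and fails, since 78 are needed.

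**4. Test with the *k* men counted as failures.** The denominator becomes 96 + k. Critical values are 73/97, 74/98, 74/99 and 77/102 for k = 1, 2, 3 and 6. With a true rate of 0.65:

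- False success is 1.8%, 1.8% and 0.7% for k = 1, 3 and 6.
- The expected rate is 96 × [0.65/(1 − k/120)]/(96 + k). For k = 6 this is 96 × 0.6842/102 = 0.644, a little under 0.65, because the other untested men are still dropped.

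**5. Power after that change, 96 tested.** This depends on which men the 80% describes. If it describes all treated men, the rate among the others is 0.80/(1 − k/120). If it describes tested men only, that rate is 0.80.

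| k | 80% of all treated men | 80% of tested men only |
|---|---|---|
| 1 | 89.7% | 86.3% |
| 2 | 88.4% | 80.2% |
| 3 | 91.6% | 80.2% |
| 6 | 88.6% | 54.1% |

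The values do not fall steadily because the critical value moves in whole steps.

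**The case against.** - **The exclusion is inferred.** A reader might take it that the plan removes every man without a device. The documents do not say so. Sections 7 and 9.4 keep ITT men in follow-up, the pad test needs no device, and section 10.9 lets pads be mailed. A man without a device who returns a test can be scored on it. This stands, and it confines the point to men with no 12-month pad weight. Even for those who return one, the reference date is undefined if they were never activated.
- **Missing data are already addressed.** A reader might infer that the plan ignores the risk. It does not: the tipping-point analysis can expose the effect. But it is a sensitivity analysis, so the primary test keeps its smaller denominator.
- **The size is assumed.** A reader might infer that the error rate is in fact inflated to 5% or 10%. The documents cannot support that, because they give no rate of abandoned implantation, non-activation or explant. The figures also assume a true rate of exactly 65%. If missingness is unrelated to outcome, the 2.5% limit holds.
- **Counting failures is not neutral.** The rule treats one group of untested men as failures and drops the others, which biases the rate slightly downward. This stands and belongs in the cost.

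**Conclusion.** The point holds, and the plan should be changed. Followed as written, the available-case default drops ITT men who have neither a working device nor a 12-month test, and the forced-failure rule reaches only revisions for efficacy reasons. If the dropped men are failures, the success rate is biased upward. Three such men in 120 would put the false-success chance at 5.0%, twice the nominal 2.5%, when the true ITT rate is 65%. The effect matters for a result close to 72/96. A result near 80% would survive up to 7 such men. All of this rests on an assumed count and on these men being failures. It does not show that the trial's conclusion would be wrong.

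**What to change.** In section 11.1.1.3:

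1. State that ITT men with no implanted or activated device, or with the device explanted and not replaced by 12 months, count as treatment failures in the primary exact binomial test if they have no 12-month pad weight.
2. State that such men who do return a test are scored on it, except that a revision for efficacy reasons remains a failure.
3. Give the reference date for 12 months in men never activated.
4. Before data review, fix which revision reasons are efficacy reasons, including whether malfunction with recurrent leakage is one.
5. Keep the tipping-point analysis for the remaining missing data.

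Use the section 11.2 definitions of ITT and As Treated, and align the section 26.2 glossary with them. The glossary currently describes ITT as a procedure begun but not finished, and As Treated as implantation attempted rather than successful.

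**Cost.** The change is wording, plus implant, activation and explant status that the trial should already hold; section 11.3.6 allows it in an amended SAP before analysis. The observed rate becomes less favourable and the test slightly conservative (expected rate 64.4% at a true 65% with 6 such men). With 96 tested and 1 to 6 such men, power is about 88% to 92% if the 80% describes all treated men, and between 86% and 54% if it describes tested men only. The sponsor should say which is meant and restate power if needed.
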